3 OBJECTIVES AND PURPOSE

Primary Objective:

To estimate the complete response rate following treatment with CPX-351. Complete remission will be evaluated by bone marrow biopsy at day 28 of therapy in all patients with medullary disease receiving at least one full cycle of CPX-351. For patients with extramedullary disease, CT or PET/CT will be used for response. Cheson criteria (2003) will be used to evaluate remission status, specifically complete remission (CR), complete remission with incomplete hematologic recovery (CRi/CRh), partial response (PR), and aplasia.

Important Secondary Objectives:

Additional clinical endpoints will include

- 1) To evaluate safety and tolerability of CPX-351 using CTCAE 5.0.
- 2) Minimal residual disease assessment (MRD) by 10 color flow cytometry and next generation sequencing (NGS) by Clonoseq (for Philadelphia negative leukemia) or PCR for BCR-ABL (for Philadelphia positive leukemia).
- 3) Progression Free Survival as defined by Cheson Criteria, namely progression, failure to respond, or death, as assessed from time of first treatment.
- 4) Overall Survival as defined by Cheson Criteria, namely death due to any cause as assessed from time of first treatment.

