4.2.2 SECONDARY ENDPOINTS

Secondary Endpoints will include

- 1) Evaluation of safety of CPX-351 using CTCAE 5.0.
- 2) Minimal residual disease assessment (MRD) by 10 color flow cytometry and next generation sequencing (NGS) by Clonoseq (for Philadelphia negative leukemia) or PCR for BCR-ABL (for Philadelphia positive leukemia) at day 28. Using a threshold of 0.01% leukemic cells, MRD provides a better estimate leukemic cell sensitivity to therapy, and correlates with both PFS and OS.
- 3) Progression Free Survival as defined by Cheson and Lugano Criteria (ref 27 and 32), namely progression, failure to respond, or death, as assessed from time of first treatment. The 12 month progression free survival rate with standard chemotherapeutic approaches in relapsed ALL is estimated at 10%. PFS is a standard estimate that accounts for response rate, response duration, and mortality to estimate therapeutic benefit in clinical trials.
- 4) Overall Survival as defined by Cheson and Lugano Criteria (ref 27 and 32), namely death due to any cause as assessed from time of first treatment. The 12 month overall survival for those with standard chemotherapeutic approaches in relapsed ALL estimated at 20%. Overall survival is a standard criteria for assessing therapeutic benefit in clinical trials.

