6.1.7 STARTING DOSE AND DOSE ESCALATION SCHEDULE

Patients will receive induction with CPX-351 at a dose of 100 u/m² administered intravenously over 90 minutes on days 1, 3 and 5 of a 28 day cycle.

This may be followed by consolidation with CPX-351 at a dose of 65 u/m² administered intravenously over 90 minutes on days 1 and 3 of a 28 day cycle.

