6.1.9 DURATION OF THERAPY

All patients completing induction will be evaluable for efficacy. Consolidation may be started at the time of hematologic recovery (28-75 days after start of induction) for those achieving a complete remission or complete remission with incomplete hematologic recovery. Consolidation cycles may be repeated at the time of hematologic recovery for a maximum total of 3 consolidation cycles.

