10.2 STATISTICAL HYPOTHESES

- All Endpoints are exploratory, and may be used to facilitate design of an expansion or subsequent phase 2 study.
- Primary Efficacy Endpoint:
 - Complete Remission and Complete Remission with incomplete hematologic recovery will serve as the primary endpoint.
- Secondary Efficacy Endpoint(s):
 - Safety
 - Minimal Residual Disease Remission Rate
 - Progression Free Survival
 - Overall Survival

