10.3 ANALYSIS DATASETS

- All patients receiving at least one dose of CPX-351 will be evaluable for safety.
- Efficacy analyses will be restricted to those receiving a full cycle of induction therapy.

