10.4.3 ANALYSIS OF THE SECONDARY ENDPOINT(S)

- Minimal Residual Disease (MRD) will be studied as a dichotomous endpoint using a cutoff of 1×10^{-4} cells/transcripts as the lower limit for residual leukemia, and presented as the percentage of patients reaching this landmark as their best response. MRD assessment will be obtained with each bone marrow biopsy assessment, as described below.
- Progression Free Survival and Overall Survival will be reported as per Cheson and Lugano Criteria, and analyzed using a standard Kaplan-Meier approach. Patients will undergo bone marrow biopsy evaluation after each cycle of therapy per standard of care to facilitated assessment. Patients achieving CR/CRi at the end of consolidation with marrow involvement will have follow-up bone marrow biopsy evaluation every 3 months in the first year following their last cycle of therapy, and every 6 months in the subsequent 2 years following their last cycle. Patients who remain in remission greater than 3 years from their last cycle of therapy will have bone marrow biopsy evaluation performed as needed. Patients without marrow involvement will have follow-up imaging (CT or PET/CT) every 3 months in the first year following their last cycle of therapy, and every 6 months in the subsequent 2 years following their last cycle. Patients progressing to allogeneic transplant following therapy will be censored at the time of conditioning.
- Safety will be continually assessed during the course of induction and consolidation cycles. Safety assessment will continue at a minimum of every 3 months for those who do not progress to allogeneic transplant or alternative therapy.

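### PFS and OS are timed from first treatment but analysed only in patients who complete induction, so a dosed patient who dies before completing is left out of both curves

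*Combined protocol and SAP*

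**What the plan says.** All references are to the combined protocol and SAP.

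- **Analysis set.** Section 10.3: "Efficacy analyses will be restricted to those receiving a full cycle of induction therapy". Section 6.1.9 gives the same condition from the other side: "All patients completing induction will be evaluable for efficacy". Only safety is assigned to patients with at least one dose.
- **Endpoints covered.** Section 10.2 places PFS and OS, with MRD and safety, under its secondary efficacy heading. Section 10.3 makes no exception for time-to-event endpoints.
- **Events and time origin.** Section 4.2.2 defines PFS by its events, "namely progression, failure to respond, or death, as assessed from time of first treatment", and OS as "namely death due to any cause as assessed from time of first treatment". Section 3 uses the same origin for both.
- **Method.** Section 10.4.3 has both endpoints "analyzed using a standard Kaplan-Meier approach". It gives no separate population, landmark, delayed entry or all-treated sensitivity analysis.
- **Meaning of a cycle.** Section 6.1.7 gives induction doses "on days 1, 3 and 5 of a 28 day cycle". No section says whether a full cycle means the three doses or the 28 days.
- **Replacement and losses.** Section 5.4.2 allows replacement of patients who drop out before the day 28 assessment, and section 10.6.1 of those who cannot complete induction. Section 10.5 expects fewer than 10% to fail to complete induction and plans for 10 evaluable patients.

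**The concern.** The clock starts at the first dose, but membership of the analysis set depends on something that happens later. A patient who is dosed and dies before completing induction meets the OS event definition and still cannot appear in the OS curve. Everyone who does appear is known to have survived until completion. This is selection on a post-baseline event, and it gives the curve a stretch of immortal time. Because such patients may be replaced, the analysed number can still be 10 and the loss need not be visible in the report.

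This is separate from the denominator of the CR/CRi rate. Counting non-completers as non-responders would settle the response rate and leave the PFS and OS curves unchanged. What is at stake is the readability of two secondary endpoints that section 10.2 says may help to design an expansion or a later phase 2 study.

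**Working it through.** **Plan's own figure.** The plan gives no sample size, power or precision for PFS or OS. Its only design calculation is the illustrative two-stage table in 10.4.2. That table reproduces by exact binomial calculation: early-termination probability 0.5138 (stated 0.514), average N 14.376 (14.38), alpha 0.0844 (0.084), beta 0.0952 (0.095). It concerns CR/CRi and is not affected by this point.

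**Inputs.** Share not completing induction: below 10% (10.5), so 10% is used as the ceiling. Reference 12-month rates: OS 20% and PFS 10% (4.2.2), used here only as illustrative true values. Window from first dose to completion: 4 days (day 1 to day 5) or about 28 days, depending on what a full cycle means (6.1.7).

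**Step 1: how often the restriction would matter.** At 10%, the expected number of dosed non-completers per 10 completers is 10 × 0.1/0.9 = 1.11. The chance of losing at least one before 10 completers are reached is 1 − 0.9^10 = 0.651.

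**Step 2: bias if those excluded are early deaths.** If a share d of treated patients dies before completion and is excluded, every later estimate is inflated: S_restricted(t) = S_all(t)/(1 − d).

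- d = 5%: OS 0.20/0.95 = 21.1%; PFS 0.10/0.95 = 10.5%.
- d = 10%: OS 0.20/0.90 = 22.2%; PFS 0.10/0.90 = 11.1%.

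In patient counts, 2 of 10 analysed alive at 12 months is 20%. Restoring one early death gives 2/11 = 18.2%, and restoring two gives 2/12 = 16.7%.

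**Step 3: dependence on the window.** Assume a constant hazard λ = −ln(S12)/365.25, with all events inside the window excluded, so that S12_restricted = S12/exp(−λt).

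| Endpoint, window | Removed before completion | 12-month estimate | Median, days |
|---|---|---|---|
| OS, 4 days | 1.7% | 20.4% (true 20%) | 157 to 161 |
| OS, 28 days | 11.6% | 22.6% (true 20%) | 157 to 185 |
| PFS, 4 days | 2.5% | 10.3% (true 10%) | 110 to 114 |
| PFS, 28 days | 16.2% | 11.9% (true 10%) | 110 to 138 |

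The 4-day PFS row is an upper bound, since a patient can progress and still receive all three doses. On that reading the immortal time for PFS is strict for death only.

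**Step 4: the opposite case.** If one excluded patient stopped for another reason and is alive at 12 months, restoring that patient turns 2/10 into 3/11 = 27.3%. The restricted estimate was then too low.

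**The case against.** The strongest reply is that the restriction was written with response in mind. Section 3 attaches the full-cycle condition to the remission evaluation, and section 10.6.1 justifies replacement by the remission rate. The secondary efficacy list in 10.2 also contains safety, which 10.3 assigns to a different set, so the heading alone does not settle which set applies. This is fair as to intent. But 10.3 exempts only safety, and no section names another set for PFS and OS.

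Several stronger readings are tempting and are not supported:

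- *28-day survival is 100% by construction.* This needs the 28-day meaning of a full cycle. Sections 10.3, 10.5 and 10.6.1 speak of therapy received, induction completed or a course completed, which favours three doses by day 5.
- *Treatment failures drop out of PFS.* Only events that prevent completion are lost. A patient who completes induction and fails to respond at day 28 stays in and counts as a PFS event.
- *Both curves are necessarily biased upwards.* This holds only if the excluded patients have early events, as step 4 shows.
- *The curves will be compared with the 10% and 20% rates.* Section 4.2.2 gives these as background. No comparison or test is specified, and the population behind them is not described.
- *Exclusion is already happening.* Section 2.3.2 reports 7 treated and a response rate of 83%, which fits 5/6 rather than 5/7 (71%). It concerns response, and the seventh patient's status is not stated.

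It also stands that the shift is small beside sampling error (the exact 95% interval for 2/10 is roughly 3% to 56%), that all endpoints are called exploratory, and that the 4-of-10 expansion rule uses CR/CRi.

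**Conclusion.** The point holds in a limited form. Taken together, 10.2, 10.3, 4.2.2 and 10.4.3 leave a dosed patient who dies before completing induction out of an OS curve that is meant to count death from any cause from first treatment. With a true 12-month OS of 20%, the distortion is about 0.4 percentage points on the three-dose reading and about 2 to 3 points at the plan's 10% ceiling or on the 28-day reading. These figures assume that the excluded patients have early events and, for the window calculation, a constant hazard. If they do not have early events, the direction can reverse. It should be corrected because the estimand and the analysis set disagree and the remedy is cheap. It does not threaten the primary endpoint or the expansion rule.

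**What to change.** 1. In 10.3, state that PFS and OS are analysed in all patients who received at least one dose of CPX-351, timed from the first dose, and that replaced patients remain in these analyses.
2. Define a full cycle of induction for analysis purposes, and use the same term in 3, 6.1.9, 10.3, 10.5 and 10.6.1.
3. If a completers-only curve is wanted, label it supplementary and start its clock at the end of induction.
4. Align the follow-up text. Section 5.4.1 ties 12-month survival follow-up to documented progression and otherwise gives disease-status follow-up of up to 30 days. Section 7.3.5 leaves procedures after early termination to physician discretion. Both should provide for recording survival status in non-completers. The plan should also state how PFS is handled without a day 28 assessment, whether as an event or censored, and on what date.

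**Cost.** The at-least-one-dose set already exists, and deaths within 30 days of the last dose fall largely inside the adverse-event window in 8.3 and 8.4.1. The edit goes beyond one sentence in 10.3 because 5.4.1 and 7.3.5 change too, and follow-up data would be needed for perhaps one or two patients. The curves will be slightly less favourable if the losses are early deaths. Treatment and sample size need not change.

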10.4 DESCRIPTION OF STATISTICAL METHODS

10.4.1 GENERAL APPROACH

This will be a phase 2 pilot trial to assess efficacy of CPX-351 in relapsed and refractory acute lymphoblastic leukemia. If 4 or more CR/CRi are observed in the first 10 patients, Jazz Pharmaceuticals will consider an increase in the budget to facilitate accrual to a total of 19 patients (ie, 9 additional subjects), possibly in a multi-center setting. This would be sufficient to test our hypothesis that CPX-351 will increase the CR/CRi rate from a historical standard of 35% to 65% (as summarized in section 2.2) using a power of 90% and type I error rate of 0.1.

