SOP	Standard Operating Procedure
UP	Unanticipated Problem
US	United States

STATEMENT OF COMPLIANCE

The trial will be conducted in accordance with the ICH E6, the Code of Federal Regulations on the Protection of Human Subjects (45 CFR Part 46). The Principal Investigator will assure that no deviation from, or changes to the protocol will take place without prior agreement from the sponsor and documented approval from the Institutional Review Board, except where necessary to eliminate an immediate hazard(s) to the trial participants. All personnel involved in the conduct of this study have completed Human Subjects Protection Training.

I agree to ensure that all staff members involved in the conduct of this study are informed of their obligation to meet the above commitments.

Principal Investigator: [name]
Print/Type Name

Signed: _____ Date: _____

STUDY SUMMARY

Title: A Single-Arm, Open-Label Phase 2 Pilot Study of Vyxeos (CPX-351) in Adults with Relapsed or Refractory Acute Lymphoblastic Leukemia.

Objectives:

Primary Objective:

- 1) To estimate the complete response rate following treatment with CPX-351

Important Secondary Objectives:

- 1) To evaluate the safety and tolerability of CPX-351
- 2) To estimate minimal residual disease burden following treatment with CPX-351
- 3) To estimate the progression free survival (PFS) following treatment CPX-351
- 4) To estimate the overall survival (OS) following treatment with CPX-351

Endpoint

Primary Endpoint:

- 1) Complete remission rate

Important Secondary Endpoints:

- 1) To evaluate the safety and tolerability of CPX-351
- 2) Minimal Residual Disease Burden
- 3) PFS
- 4) OS

Population:

Patients ≥ 18 years old with relapsed acute lymphoblastic leukemia (ALL) who are registered at the Moffitt Cancer Center.

Phase:

2, pilot

Number of Sites enrolling participants:

1

Description of Study

Agent :

- 1) Induction: Vyxeos (CPX-351), 100 units/m² days 1, 3, & 5
- 2) Consolidation: Vyxeos (CPX-351) 65 units/m² days 1 & 3 (up to 3 cycles)

Study Duration:

[figure not shown]
24 months

Participant Duration:

30 months

SCHEMATIC OF STUDY DESIGN

Induction	CPX-351 100 u/m ² 90 minute infusion days 1,3,5
Consolidation Per section 7.3.2.11	CPX-351 65 u/m ² 90 minute infusion days 1,3 (administered 35-75 days after start of induction) for up to 3 cycles.

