2 INTRODUCTION: BACKGROUND INFORMATION AND SCIENTIFIC RATIONALE

2.1 BACKGROUND INFORMATION

Outcomes are poor among adults with relapsed and refractory ALL, with most chemotherapy regimens demonstrating a CR rate of ~40%, coupled with a median EFS of ~6mo. (ref 1-10). To this end, several

novel therapies have emerged, including blinatumomab (CR/CRi rate 43%, med OS 7.7mo), inotuzumab ozagomycin (CR/CRi rate 80.7%, med OS 7.7mo), and liposomal vincristine (CR/CRi rate 20%, 6mo OS 35%). (ref 11-13). While these therapies have advanced the management of relapsed ALL, relapse and shortened life expectancy remain the expectation for most patients.

Chemotherapy resistance has been related in part to the overexpression of cell proteins implicated in drug transmembrane transport, such as PGP and LRP. (ref 14-18). Attempts to intensify therapy by increasing anthracycline dose or with the use of novel anthracycline derivatives have not significantly improved outcome. (ref 8-9,19). More recently, trials using liposomal daunorubicin in conjunction with high dose cytarabine demonstrated improved clinical efficacy (CR 80%, 12mo OS 39%). Notably, in cells from those with increased expression of multi-drug resistant proteins (72% of patients), the in vitro retention of liposomal daunorubicin and subsequent apoptosis were both significantly higher, when compared with free daunorubicin. (ref 18) Recent work further suggests molar ratio of cytarabine:daunorubicin, in addition to drug uptake, may be important in yielding therapeutic response. (ref 20-21)

CPX-351 (or Vyxeos) is a liposomal formulation of cytarabine and daunorubicin at a fixed molar ratio. A randomized study of CPX-351 (vs non-liposomal cytarabine and daunorubicin) in high risk acute myeloid leukemias demonstrated a significant benefit in complete remission rates (47.7% vs 33.3%) and median overall survival (9.56 vs. 5.95 months), culminating in FDA approval August 2017.

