2.2 RATIONALE

Remission rates vary considerably depending on population studies (children vs adults), relapsed vs refractory status, and timing of salvage (first relapse vs beyond first relapse) making it difficult to extrapolate baseline rate. If focusing specifically on 2 trials that used an induction composed of cytarabine (3gm/m² x5d) and idarubicin (40mg/m² on d3), complete remission rates are approximately 40% (38-44%, total n=54). (ref 4-5). Alternatively, a more recent phase 3 trial of inotuzumab vs standard of care in patients in first or second relapse shows a composite CR rate in the standard of care arm (Cytarabine+Mitoxantrone, high dose Cytarabine, and Fludarabine, Cytarabine, and GCSF, total n=109) of 29%. (ref 13). Given these data, it is determined that a baseline CR rate of 35% is likely to estimate activity with a standard salvage regimen.

Data using liposomal anthracyclines among those with relapsed ALL, including FLAD (Fludarabine, Cytarabine, Liposomal Daunorubicin) and Cytarabine+Liposomal Daunorubicin, have shown an improvement in CR rates, at 65% and 80%, respectively. (ref 18,28) Together these data suggest a CR rate of 65% should be attainable using CPX-351.

However, at this stage, a phase 2 pilot trial is proposed to explore response rates among 10 patients with ALL. Should sufficient activity be observed, consideration may be made in consultation with Jazz

Pharmaceuticals, to increase the budget to increase accrual to formally test our hypothesis, possibly in a multicenter setting.

Safety will be monitored as per standard routine, accounting for adverse events using CTCAE v. 5.0. Myelotoxicity is anticipated, in addition to associated infections. Frequency of these events will be monitored for comparison with historical rates, referencing against historical regimens noted above. Adverse events of special interest include bone marrow aplasia (hypocellular marrow without adequate count recovery >42 days from start of therapy), and *symptomatic* heart failure (accompanied by a decrease in the ejection fraction >10% from baseline greater than 42 days from start of therapy).

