4.2 STUDY ENDPOINTS

4.2.1 PRIMARY ENDPOINT

- We will measure remission rate at day 28 to address the primary endpoint of complete remission (with or without complete hematologic recovery), as defined by Cheson Criteria (ref 27). For those with extramedullary disease, Lugano criteria will be used to assess response (ref 32). This is a standard assessment of drug efficacy for phase 2 clinical trial design in acute leukemias, as response correlates closely with progression free- and overall survival (PFS and OS).

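### The 35% and 65% rates are derived as CR rates but used as CR/CRi rates, so they are not shown to match the endpoint behind the 4-of-10 rule

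*Combined protocol and SAP*

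**What the plan says.** **Endpoint.** Section 10.2 counts both categories: "Complete Remission and Complete Remission with incomplete hematologic recovery will serve as the primary endpoint". Section 4.2.1 agrees, naming a "primary endpoint of complete remission (with or without complete hematologic recovery"). The expansion rule in 10.4.1 and 10.4.2 likewise needs at least 4 CR/CRi among the first 10 patients. The Study Summary and section 3 word the primary objective more narrowly: "To estimate the complete response rate following treatment with CPX-351".

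**Benchmark.** Section 10.4.1 hypothesises that "CPX-351 will increase the CR/CRi rate from a historical standard of 35% to 65% (as summarized in section 2.2"). In section 2.2 the null rate reads: "it is determined that a baseline CR rate of 35% is likely to estimate activity with a standard salvage regimen". The target reads: "Together these data suggest a CR rate of 65% should be attainable using CPX-351". No rate in section 2.2 is labelled CR/CRi.

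**The protocol's own use of the terms.** Section 2.1 reports some agents on the broader measure, for example "blinatumomab (CR/CRi rate 43%, med OS 7.7mo"), and others, including liposomal daunorubicin with cytarabine, as CR. Section 3 and Appendix A list CR and CRi as separate categories.

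**The concern.** CRi is an additional response category, so a CR/CRi rate cannot be lower than the CR rate in the same patients. A decision rule is calibrated only if the historical rate and the trial's count use one definition. Here the count is CR/CRi, while the cited section offers rates called CR, one of which may be CR/CRi under another name.

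The 4-of-10 rule is the pilot's one decision rule, and with 10 patients a single CRi turns 3 of 10 into 4 of 10. Section 8.4.4 also says liposomal delivery may delay or prevent count recovery, and incomplete recovery is what separates CRi from CR. A sizeable CRi share is therefore plausible on the protocol's own account. If the benchmark does not match the endpoint, the stated alpha of 0.084 and beta of 0.095 do not describe the comparison that will be made.

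**Working it through.** **1. Reproduce the plan's figures.** The inputs, from 10.4.1 and 10.4.2, are n1 = 10, r1 = 3, N = 19, r = 9, null rate 0.35 and target rate 0.65. X1 is the number of responders in the first 10 and X2 the number in the next 9, both binomial.

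- PET = P(X1 ≤ 3 | 10, 0.35) = 0.0135 + 0.0725 + 0.1757 + 0.2522 = 0.514 after rounding.
- Average N = 10 + (1 − 0.5138) × 9 = 14.38.
- Rejection probability at rate p = Σ over x = 4 to 10 of P(X1 = x | 10, p) × P(X2 ≥ 10 − x | 9, p). This is 0.084 at p = 0.35 and 0.905 at p = 0.65, so beta is 0.095.

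All four agree with the table in 10.4.2. The arithmetic is sound, and the question is only what 35% and 65% measure.

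**2. Trace the inputs in section 2.2.**

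| Input | Rate | n | Label in 2.2 | Could it include CRi? |
|---|---|---|---|---|
| Two cytarabine/idarubicin trials | 38-44%, about 40% | 54 | complete remission | Not stated |
| Standard-of-care arm of the inotuzumab phase 3 trial | 29% | 109 | composite CR | Possibly: 2.1 reports this trial's inotuzumab arm as CR/CRi |
| Two liposomal daunorubicin regimens | 65% and 80% | not given | CR | Not stated |

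Composite could mean CR plus CRi, or it could mean pooled over the three control regimens listed beside it. The text does not say. The 29% arm supplies 109 of 54 + 109 = 163 benchmark patients, about two thirds.

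Section 2.2 does not say how 35% was reached. The patient-weighted mean is (54 × 0.40 + 109 × 0.29) / 163 = 53.21 / 163 = 0.326. The simple mean of 40% and 29% is 34.5%. If the two sources use different definitions, either average mixes them.

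**3. Sensitivity of the rule.** The documents give no CRi fraction for any historical regimen, so the true historical CR/CRi rate is an assumption here. The 4-of-10 rule and the 10-of-19 rejection rule are held fixed. Each row gives the chance that a drug no better than that historical rate passes.

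| Assumed historical CR/CRi rate | P(at least 4 of 10) | Type I error of the two-stage design |
|---|---|---|
| 29% (the composite figure taken as CR/CRi) | 0.324 | 0.025 |
| 35% (as planned) | 0.486 | 0.084 |
| 40% | 0.618 | 0.180 |
| 45% | 0.734 | 0.320 |
| 50% | 0.828 | 0.489 |

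**4. The target.** If 65% is a CR-only rate, the matching CR/CRi target is higher. At an assumed 70%, the same formula gives power 0.963 instead of 0.905, so the stated power would be understated.

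**5. How much CRi can add.** Sections 3 and 4.2.1 place the primary assessment at day 28. Appendix A does not allow CRi to be declared before day 35. Read literally, no CRi can count at the primary timepoint. If later assessments count, the endpoint is broader than CR.

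**The case against.** A reader might infer that the benchmark is CR-only, so that the rule is bound to be too lenient and the false-positive rate is really 0.18 to 0.49. The documents do not support this, for three reasons.

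- The larger null source is called composite and comes from a trial that section 2.1 reports as CR/CRi, so most of the benchmark patients may already be on the broader measure. If 29% were the right CR/CRi rate, the rule would be conservative, with type I error 0.025.
- A CR label does not prove that a source excluded CRi. Section 4.2.1 itself uses complete remission to cover patients with and without full count recovery.
- The day 35 restriction leaves it open whether CRi adds anything at day 28.

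It can also be said that little hangs on the point. All endpoints are declared exploratory, the Simon table is offered as an illustration, and in 10.4.1 reaching 4 of 10 only leads the drug supplier to consider more funding.

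These arguments rule out a directional claim and limit the consequence. They do not remove the mismatch. Section 10.4.1 still cites section 2.2 for a measure that section 2.2 does not report, 10.4.2 makes expansion depend on the rule, and 10.4.1 presents 19 patients as enough to test the 35% versus 65% hypothesis at the stated error rates.

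**Conclusion.** The mismatch of labels is established: 35% and 65% are derived as CR rates and used as CR/CRi rates. The benchmark is not shown to match the endpoint, and it may mix two definitions. The direction and size of any error cannot be settled from the documents.

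Over assumed historical CR/CRi rates of 29% to 50%, the chance that a drug no better than history passes 4 of 10 runs from 0.324 to 0.828. The type I error runs from 0.025 to 0.489, against the plan's limit of 0.1. A shift of only 5 points above 35% gives 0.180. These figures show sensitivity and do not estimate the actual error rate. The point bears on the expansion decision and its stated operating characteristics, not on the validity of the pilot's response estimate.

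**What to change.** 1. In section 2.2, identify each cited rate as CR or CR/CRi from its source, say what composite means for the 29%, and show how 35% was reached.
2. In 10.4.1, put the null and target rates on the endpoint's definition, and restate alpha and power in 10.4.2 if either changes. Where a source reports CR only, compare it with the trial's CR-only rate.
3. Report CR and CR/CRi as separate lines in the primary result, each beside its matching benchmark.
4. Align the primary objective in the Study Summary with 4.2.1 and 10.2.
5. Reconcile the day 28 assessment in sections 3 and 4.2.1 with the day 35 restriction on CRi in Appendix A.

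The cost is protocol wording and a re-reading of sources already cited. No new data are needed, because Appendix A already classifies CR and CRi separately. The downsides are that some sources may not report CRi, in which case only the CR comparison is available, and that the stated benchmark, alpha or power may become less favourable.
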